## **7. Treatments**

Study treatment is defined as any investigational treatment(s), marketed product(s), placebo, or medical device(s) intended to be administered to a study participant according to the study protocol.

Clinical supplies [study treatment(s) provided by the Sponsor] will be packaged to support enrollment and replacement participants as required. When a replacement participant is required, the Sponsor or designee needs to be contacted prior to dosing the replacement supplies. Clinical supplies will be affixed with a clinical label in accordance with regulatory requirements.

### **7.1 Treatments Administered**

The study treatment(s) to be used in this trial are outlined below in [Table 3](#).

Table 3 Study Treatment

Study Treatment Name	Dosage Formulation	Unit Dose Strength(s)	Dose Frequency	Dosage Level(s)	Route of Administration	Regimen/ Treatment Period	Sourcing
MK-7162	Oral Compressed Tablet (OCT)	1, 10, and 100 mg potency tablets	QD	25 mg up to 400 mg	Oral	Cycles 1-36; 21-day treatment cycle	Provided centrally by the Sponsor.
Pembrolizumab (MK-3475)	Solution for Infusion	100 mg/4 mL	Q3W	200 mg	IV infusion	Cycles 2-36: Day 1 of each 21-day treatment cycle	Provided centrally by the Sponsor.

For pembrolizumab combination treatment-day visits, MK-7162 should be administered in clinic a minimum of 1 h prior to initiation of pembrolizumab infusion.

All supplies indicated in [Table 3](#) will be provided per the ‘Sourcing’ row depending upon local country operational requirements. Every attempt should be made to source these supplies from a single lot/batch number. The trial site is responsible for recording the lot number, manufacturer, and expiry date for any locally purchased product as per local guidelines unless otherwise instructed by the Sponsor.

Refer to section 9.1.8 for details regarding administration of the study treatment.

## **7.2 Dose Modification (Escalation/Titration/Other)**

### **7.2.1 Dose Administration/Escalation/Cohort Expansion**

#### **7.2.1.1 Dose Administration (Preparation)**

Details on preparation and administration of MK-7162 and pembrolizumab are provided in the appropriate Pharmacy/Procedures Manual.

#### **7.2.2 Definition of Dose Limiting Toxicity**

All toxicities will be graded using CTCAE Version 4.0 based on the investigator assessment.

In this study, the DLT window of observation will be during the first 6 weeks of treatment (Cycles 1 and 2). The occurrence of any of the following toxicities will be considered a DLT, if assessed by the investigator to be possibly, probably, or definitely related to study drug administration, excluding toxicities clearly not related to the drug, such as disease progression, environmental factors, unrelated trauma, etc.:

1. Grade 4 nonhematologic toxicity (not laboratory)
2. Grade 4 hematologic toxicity lasting  $\geq 7$  days, except thrombocytopenia:
  - Grade 4 thrombocytopenia of any duration
  - Grade 3 thrombocytopenia associated with bleeding.
3. Any nonhematologic AE  $\geq$ Grade 3 in severity should be considered a DLT, with the following exceptions: Grade 3 fatigue lasting  $\leq 3$  days; Grade 3 diarrhea, nausea, or vomiting without use of anti-emetics or anti-diarrheals per standard of care; Grade 3 fever and Grade 3 flu-like symptoms lasting  $\leq 24$  hours with negative infectious disease workup (including negative blood and urine cultures)
4. Any Grade 3 or Grade 4 non-hematologic laboratory value if:
  - Clinically significant medical intervention is required to treat the participant, or
  - The abnormality leads to hospitalization, or
  - The abnormality persists for  $>1$  week
  - The abnormality results in a Drug-induced Liver Injury (DILI) (see Sections 9.3.1 and 9.3.7 for criteria)

Exceptions: Clinically nonsignificant, treatable, or reversible laboratory abnormalities including liver function tests, uric acid, etc.

5. Febrile neutropenia Grade 3 or Grade 4
  - Grade 3 is defined as ANC <1000/mm^3 with a single temperature of >38.3 degrees C (101 degrees F) or a sustained temperature of ≥38 degrees C (100.4 degrees F) for more than 1 hour
  - Grade 4 is defined as ANC <1000/mm^3 with a single temperature of >38.3 degrees C (101 degrees F) or a sustained temperature of ≥38 degrees C (100.4 degrees F) for more than 1 hour, with life-threatening consequences and urgent intervention indicated.
6. Any treatment-related toxicity that causes the participant to discontinue treatment during Cycle 1 or Cycle 2
7. Prolonged delay (>2 weeks) in initiating Cycle 2 or Cycle 3 due to treatment-related toxicity
8. Missing >25% of MK-7162 doses as a result of drug-related AE(s) during the first 2 cycles of treatment
9. Grade 5 toxicity

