Vital Signs	X	X		X		X		X	X	X	X			
Consists of temperature, pulse, respiratory rate, blood pressure, and oxygen (O2) saturation.
 
C1D1: Predose: Obtain within 1 h (± 30 min) prior to MK-7162 dose; Postdose: Obtain 2, 4, 6, and 8 h (± 30 min) after dosing
 
C2D1: Predose: Obtain within 1 hour (± 30 min) prior to MK-7162 dose; Postdose: Obtain 2, 4, 6, and 8 h (± 30 min) after completion of MK-7162 and pembrolizumab dosing
 
C3D1 and beyond: Predose: Obtain within 1 h (± 30 min) prior to MK-7162 dose.

12-lead ECG	X	X		X						X				
C1D1 Postdose: Obtain within 30 min after dosing
 
C2D1 Postdose: Obtain within 30 min after the end of the pembrolizumab infusion

Eastern Cooperative Oncology Group (ECOG) Status	X	X		X		X		X	X	X	X			Assessment to confirm eligibility must be performed within 7 days prior to C1D1 dosing

Trial Phase:	Screening	Treatment (Treatment Cycle = 21 days)							End of Treatment (EoT)	Post-treatment		Notes
		MK-7162 Mono-therapy		MK-7162 and Pembrolizumab Combination Therapy						Last Dose / Discontinuation	Safety Follow-up	
Visit or Cycle (C):	C1		C2		C3		C4	C5 thru C36	30 days after the last dose	Every 12 weeks after the last dose		
Scheduling Day (D):	D1	D15	D1	D15	D1	D15	D1	D1				
Schedule Window (Days):	-28 to -1		± 3	± 3	± 3	± 5	± 3	± 3	± 7	± 7	± 14	
Safety: Local Laboratory Evaluations												

Screening: Obtain and evaluate clinical laboratory tests within 7 days prior to first dose of study medication (C1D1) unless otherwise specified. Tests performed prior to the participant signing IC as part of routine clinical management are acceptable in lieu of a screening test, if the test is performed within the specified time frame.
 
Day 1 for All Treatment Cycles: Obtain samples prior to MK-7162 and pembrolizumab dosing, unless otherwise specified
 
See Procedures Manual for details regarding collection and management of samples
												
HIV, Hepatitis B and C screen	X											Historical results are acceptable unless testing is required by local regulation. Tests performed during the 28 day screening period are acceptable.
Hematology	X	X		X		X		X	X	X	X	
Urinalysis	X	X		X		X		X		X		
Comprehensive Chemistry Panel	X	X		X		X		X	X	X		
Lipase and Amylase	X									X		
LDH, GGT	X	X		X		X		X	X			

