Scheduling Day (D):		D1	D15	D1	D15	D1	D15	D1	D1				
Schedule Window (Days):	-28 to -1		± 3	± 3	± 3	± 3	± 5	± 3	± 3	± 7	± 7	± 14	
Plasma for MK-7162 Pharmacokinetics (PK)		X	X	X	X	X	X	X	X	X	X		C1D1 & C1D15: Predose: Obtain following an overnight fast. Postdose: 1, 2, 4, and 8 hrs. Participant to remain fasting for 1 hr subsequent to dosing. C2D1: Predose: Obtain following an overnight fast. Obtain same day as tumor biopsy. C2D15: Predose: Obtain following an overnight fast. C3D1: Predose: Obtain following an overnight fast. Postdose: 1, 2, 4, and 8 hrs. Participant to remain fasting for 1 hr subsequent to MK-7162 dosing. C3D15: Predose: Obtain following an overnight fast. Obtain on the same day as tumor biopsy. C4D1-C36D1: Predose every 4 cycles: C4, C8, C12, etc. Obtain following an overnight fast. Collection time point windows: 1 hr. (± 15 min), 2-8 hrs. (± 30 min)
Serum for Pembrolizumab Pharmacokinetics (PK)				X		X		X	X	X	X		C2D1: Predose; Postdose: 0.5 hrs. (± 5 min) following completion of pembrolizumab infusion C3D1: Predose C4D1-C36D1: Obtain predose every 4 cycles: C4, C8, C12, etc.

Trial Phase:	Screening	Treatment (Treatment Cycle = 21 days)								End of Treatment (EoT)	Post-treatment		Notes	
		MK-7162 Mono-therapy		MK-7162 and Pembrolizumab Combination Therapy							Safety Follow-up	Survival Follow-up		
		C1		C2		C3		C4	C5 thru C36		30 days after the last dose	Every 12 weeks after the last dose		
Scheduling Day (D):		D1	D15	D1	D15	D1	D15	D1	D1					
Schedule Window (Days):	-28 to -1			± 3	± 3	± 3	± 5	± 3	± 3	± 7	± 7	± 14		
Serum for Anti-pembrolizumab Antibodies				X		X		X	X	X	X		C2D1 and C3D1: Predose C4D1-C36D1: Obtain predose every 4 cycles: C4, C8, C12, etc.	
Blood for Plasma Pharmacodynamic (PD) and Biomarker Analyses	X	X	X	X		X	X						Screening: Obtain on the same day as the Screening tumor biopsy. Obtain following an overnight fast. C1D1 & C1D15: Predose: Obtained following an overnight fast. Postdose: 1, 2, 4, and 8 hrs. C2D1: Predose: Obtain following an overnight fast. Obtain on the same day as tumor biopsy. C3D1: Predose: Obtained following an overnight fast. Postdose: 1, 2, 4, and 8 hrs. C3D15: Predose: Obtain following an overnight fast. Obtain the same day as tumor biopsy. Collection timepoint windows: 1 hr. (± 15 min), 2-8 hrs. (± 30 min)	

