### 7.3 Method of Treatment Assignment

Study treatment will be allocated via IVRS. Each new dose level will open for enrollment without delay once the 42-day DLT observation period of the previous dose cohort is completed, and a dose escalation decision is made.

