##### **9.1.8.1.2 Timing of Dose Administration for Pembrolizumab**

The first dose of pembrolizumab is administered on C2D1. Pembrolizumab is administered once every 21 days during a morning visit in the clinic. Details on administration of pembrolizumab are provided in the appropriate Pharmacy/Procedures Manual. Refer to Section 7.2.4 (Timing of Dose Administration) for dose and treatment details.

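### The 42-day DLT window closes before a Cycle 3 delay can count as a DLT and before the first required post-pembrolizumab safety labs, and escalation need not wait for either

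*Combined protocol and SAP*

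**What the plan says.** **Window.** Section 7.2.2: "the DLT window of observation will be during the first 6 weeks of treatment (Cycles 1 and 2". The synopsis gives the same period as 42 days. Section 10.5.1 makes a participant DLT-evaluable after 42 days of safety observation, or on a DLT earlier than 42 days after the first dose. Section 5.1.1 words evaluability differently: both cycles completed, or treatment stopped for a DLT.

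**Criteria.** Criterion 6: "Any treatment-related toxicity that causes the participant to discontinue treatment during Cycle 1 or Cycle 2". Criterion 7: "Prolonged delay (>2 weeks) in initiating Cycle 2 or Cycle 3 due to treatment-related toxicity".

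**Treatment and labs.** Section 9.1.8.1.2: "The first dose of pembrolizumab is administered on C2D1". For Day 1 of every cycle the Schedule of Activities says "Obtain samples prior to MK-7162 and pembrolizumab dosing, unless otherwise specified". Its hematology row and its "Comprehensive Chemistry Panel" row are marked at C1D1, C2D1, C3D1 and C4D1, and are blank at C1D15 and C2D15. Section 9.5.4.1 and Appendix 2 let these samples be taken up to 72 hours before dosing; they do not require it.

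**Opening the next level.** Section 7.3: "Each new dose level will open for enrollment without delay once the 42-day DLT observation period of the previous dose cohort is completed". The same sentence adds that a dose escalation decision must have been made. It does not say which results that decision must have in hand.

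**The concern.** The Cycle 3 limb of criterion 7 is part of the DLT definition, yet it can only mature after the period in which DLTs are counted. Criterion 6 has a similar edge. Section 7.2.4 bases dose modifications on the previous cycle, so a toxicity arising in Cycle 2 will often be acted on at the C3D1 visit. Whether a stop made then falls within Cycle 2 is left open. The first required laboratory look at the combination falls at the same visit.

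DLT incidence is the primary safety endpoint and drives every mTPI decision, and each planned dose is twice the one before (25, 50, 100, 200, 400 mg). If the 42-day rule is followed literally, a participant on a toxicity hold at Day 43 is scored as a non-DLT and the cohort can be escalated on that score.

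**Working it through.** **Inputs.** 21-day cycles with first dose on Day 1; C3D1 visit window of 3 days either way (Schedule of Activities); 72-hour early-draw allowance (9.5.4.1); at least 7 days between participants 1 and 2 and at least 3 between 2 and 3 (5.1.1); Table 1.

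**The plan's own figure.** 2 × 21 = 42 days, which reproduces.

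**Calendar.**
- C2D1 = 1 + 21 = Day 22. Its labs are taken before the first pembrolizumab dose.
- C3D1 = 1 + 42 = Day 43. This is exactly 42 days after the first dose, so an event found that day is not earlier than 42 days under 10.5.1.
- C3D1 labs: Days 40 to 43 with the visit on schedule. The earliest possible is Day 37 (visit on Day 40, draw 3 days before).
- Criterion 7, Cycle 2: the first day with a delay over 14 days is 22 + 15 = Day 37, inside the window.
- Criterion 7, Cycle 3: 43 + 15 = Day 58, which is 58 − 42 = 16 days after the window. With the visit window it is Day 55 to Day 61, always outside.
- Duration limbs for an abnormality first seen on Day 43: Grade 4 hematologic toxicity of at least 7 days (criterion 2) is met at about Day 49 or 50; a laboratory value lasting more than 1 week (criterion 4) at about Day 51.

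**Where a cohort stands at minimum spacing.** When participant 3 reaches Day 42:

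| Participant | Study day | Days until Day 58 |
|---|---|---|
| 1 | 42 + 3 + 7 = 52 | 6 |
| 2 | 42 + 3 = 45 | 13 |
| 3 | 42 | 16 |

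None has reached Day 58. Participants 1 and 2 are past nominal C3D1, so the laboratory gap is mainly participant 3's; the criterion 7 gap can affect all three. If the next level opened with no lag, its participants could be dosed 0, 7 and 10 days later, on participant 3's Days 42, 49 and 52, all before Day 58.

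**Effect on the decision.** Recomputing the mTPI rule with Beta(1,1), target 0.30, both epsilons 0.03 and an assumed exclusion cutoff of 0.95 matches every Table 1 cell for n = 3 to 6. Effect of one DLT counted late:

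| n | Decisions for 0, 1, 2, … DLTs | One-DLT steps that change the decision |
|---|---|---|
| 3 | E, S, D, DU | 3 of 3 |
| 4 | E, S, S, DU, DU | 2 of 4 |
| 5 | E, S, S, D, DU, DU | 3 of 5 |
| 6 | E, E, S, S, DU, DU, DU | 2 of 6 |

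**The case against.** **The next cohort starts on monotherapy.** This is the strongest point, and it stands. A reader might infer that participants could receive the combination at the doubled dose before the evidence is due. On the nominal calendar they could not. A participant first dosed on the previous cohort's Day 42 gets pembrolizumab 21 days later, on Day 63 (Day 60 with the visit window), after Day 43 and after nominal Day 58. What comes early is MK-7162 alone at twice the dose. The margin is 63 − 58 = 5 days, which visit windows can use up.

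**Section 7.3 also requires a decision.** True, and the team may choose to wait. Sections 5.1.1 and 10.7 speak of combined data and continuous review. None of this obliges the decision to wait for C3D1 labs or a held Cycle 3, and 7.3 asks for no delay once its conditions are met.

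**A sensible reader would count C3D1 findings.** Labs must be reviewed and acceptable before each dose (9.5.4.1), so a stop on C3D1 predose results precedes any Cycle 3 dose and is arguably still in Cycle 2. Criterion 7 names Cycle 3, so that limb may be meant to count late. These are reasonable readings, but 10.5.1 points the other way and no text says which prevails.

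**Labs may exist inside the window.** They may: early draws and unscheduled tests are allowed. The claim is only that none is required there.

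**Cycle 2 toxicity in general is not missed.** Correct. Symptomatic events, missed doses, stops during Cycle 2 and the Cycle 2 limb of criterion 7 can all be captured by Day 42.

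**Conclusion.** The concern holds for laboratory-defined and delay-defined DLTs. The Cycle 3 limb of criterion 7 cannot be met inside the stated window on any permitted visit timing. Criterion 6 is unclear at the C3D1 visit, and escalation is not tied to either result. In a cohort of three, one such DLT turns 0/3 (escalate) into 1/3 (stay). New participants could then start twice the MK-7162 dose while that DLT is pending.

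The calendar rests on nominal visits and minimum cohort spacing; the 0-, 7- and 10-day dosing assumes no lag between decision, allocation and first dose. Three stronger inferences are not supported:

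- A rate of missed DLTs. The documents give no frequency for such events. Section 3.2.1.1 reports a dose-limiting Grade 3 autoimmune hepatitis with an IDO1 inhibitor of similar mechanism plus an anti-PD-1 antibody, which shows the type of event is plausible but not how often it would occur here.
- That any late DLT reverses the decision. This is so only at n = 3; at n = 6, moving from 0 to 1 DLT still gives escalate.
- That mid-cycle safety labs are needed. That is a monitoring choice, and the conflict can be resolved without them.

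**What to change.** **Sections 7.2.2 and 10.5.1**, add:

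> The DLT period runs through completion of the C3D1 predose assessment. A treatment-related toxicity with onset by then counts as a DLT if it leads to a stop of study treatment before the first Cycle 3 dose (criterion 6), leads to a Cycle 3 delay of more than 2 weeks (criterion 7), or meets a duration limb of criterion 2 or 4 within 2 weeks of planned C3D1. The criterion 4 exceptions are unchanged.

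**Section 7.3**, add:

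> No escalation until C3D1 predose hematology and chemistry have been reviewed for every evaluable participant who has not already had a DLT. A participant whose Cycle 3 is on hold for treatment-related toxicity, or who has a potential duration-based DLT, is pending until it resolves, treatment stops, or 2 weeks have passed.

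The 2-week limit covers the duration limbs worked out above and keeps late events from reopening completed decisions.

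**Cost.** Wording in three sections and no new procedure. The usual wait is 1 to 4 days beyond Day 42 (C3D1 on Days 43 to 46), and about 2 weeks (Day 58 at most, 16 days on the nominal calendar) only when a participant is pending. If Cycle 2 started late, C3D1 moves with it: a 14-day delay puts C3D1 at Day 57. Section 5.1.1 already asks that both cycles be complete in that case.

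**If dose finding is complete**, list in the clinical study report the events with onset by the C3D1 predose assessment that met a DLT criterion later, and show each Table 1 decision with and without them.

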### **7.2.3 Timing of Dose Administration**

#### **7.2.3.1 Timing of Administration for MK-7162**

MK-7162 will be administered once a day. The reason for any variability in administration of MK-7162 outside of the protocol-specified window should be documented in the participant's chart and recorded on the electronic Case Report Forms (eCRFs).

Every effort should be made to begin the first dose of study treatment on the day of allocation, but if this is not achieved, trial therapy should be initiated no later than 3 days from the date the study treatment cohort is allocated. All study treatments will begin on Day 1 of each cycle after all predose study procedures and assessments have been completed as detailed in Section 2 - Summary of Activities. On Day 1 of each cycle (Cycles 2-36), MK-7162 should be administered in the clinic a minimum of 1 hour prior to initiation of pembrolizumab infusion.

The Pharmacy Manual contains specific instructions for MK-7162 administration.

All study medications will be administered on an outpatient basis.

#### **7.2.3.2 Timing of Administration for Pembrolizumab**

Trial treatment of pembrolizumab should be administered on Day 1 of each 3 week cycle, beginning at Cycle 2, after all procedures/assessments have been completed as detailed in the Trial Flow Chart (Section 2).

Trial treatment of pembrolizumab may be administered up to 3 days before or after the scheduled Day 1 of each cycle due to administrative reasons.

The Pharmacy Manual contains specific instructions for pembrolizumab administration.

All study medications will be administered on an outpatient basis.

#### 7.2.4 Guidelines for Dose Modification due to Adverse Events

Adverse events (both nonserious and serious) associated with MK-7162 and pembrolizumab exposure may represent an immunologic etiology. These AEs may occur shortly after the first dose or several months after the last dose of treatment.

CTCAE 4.0 must be used to grade the severity of adverse events. The investigator may attribute each toxicity event to MK-7162 alone, to pembrolizumab alone, or to the combination, and modify the dose according to [Table 4](#) and [Table 5](#). If a dose modification for toxicity occurs with MK-7162, the dose may not be re-escalated to the dose that preceded the dose modification. Dose modifications are always based on the previous cycle.

Reduction or holding of 1 agent and not the other agent is appropriate if, in the opinion of the investigator, the toxicity is clearly related to 1 of the study medications and Sponsor consultation and approval is obtained. For example, if MK-7162 is held due to an adverse event attributed to that drug, then pembrolizumab may continue to be administered in consultation with the Sponsor. Appropriate documentation is required regarding the drug to which the investigator is attributing the adverse event. If, in the opinion of the investigator, the toxicity is related to the combination of 2 or more agents, then the corresponding drugs should be held according to recommended dose modifications.

##### 7.2.4.1 Dose Modification for MK-7162

Participants may have up to 2 dose modifications of MK-7162 throughout the course of the study, as described in [Table 4](#). If further toxicity occurs or the criteria for resuming treatment are not met, the participant must be discontinued from the attributed study treatment. If a participant experiences several toxicities and there are conflicting recommendations, the most conservative dose adjustment recommendations (dose reduction appropriate to the most severe toxicity) should be followed.

Exceptional circumstances to the following dose modification tables below may be considered after consultation with and approval by the Sponsor.

**Table 4 MK-7162 Dose Modification and Treatment Discontinuation Guidelines for Drug-Related Adverse Events**

Toxicity	Hold Treatment	Criteria for Restarting Treatment	Dose/Schedule for Restarting Treatment	Criteria for Discontinuation after Consultation with Sponsor
Hematological toxicities:				
• Any Grade 1 hematological toxicity	No	N/A	N/A	N/A
• Any Grade 2 hematological toxicity, or Grade 3 toxicity that persists for ≤5 days	Per medical assessment of the investigator	If treatment held, may be restarted when AE resolves back to baseline or to Grade 1	Per medical assessment of the Investigator: may decrease dose by 1 dose level	If AE persists for 12 weeks without resolution following reduction in dose
• Any Grade 3 hematologic toxicity that persists for >5 days, or Grade 4 hematological toxicity • Febrile neutropenia • Grade 3 thrombocytopenia of any duration if associated with bleeding	Yes	Treatment may be restarted when AE resolves back to baseline or to Grade 1	Decrease dose by 1 dose level	If AE persists for 12 weeks without resolution following reduction in dosing schedule  Permanent discontinuation should be considered for any severe or life-threatening event
Nonhematological toxicities:				
Toxicity	Hold Treatment	Criteria for Restarting Treatment	Dose/Schedule for Restarting Treatment	Criteria for Discontinuation after Consultation with Sponsor
• Any Grade 1 nonhematological toxicity • Grade 2 alopecia • Grade 2 fatigue	No	N/A	N/A	N/A
• Any Grade 2 nonhematological toxicity except Grade 2 alopecia and Grade 2 fatigue	Per medical assessment of the investigator	If treatment held, may be restarted when AE resolves back to baseline or to Grade 1	Per medical assessment of the Investigator: may decrease dose by 1 dose level	If AE persists for 12 weeks without resolution following reduction in dose

Toxicity	Hold Treatment	Criteria for Restarting Treatment	Dose/Schedule for Restarting Treatment	Criteria for Discontinuation after Consultation with Sponsor

 
Any Grade 3 or 4 nonhematological toxicity (not including laboratory, unless clinically significant medical intervention is required to treat the participant, or the abnormality leads to hospitalization, or the abnormality persists for >1 week)
 
	Yes	Treatment may be restarted when AE resolves back to baseline or to Grade 1	Decrease dose by 1 dose level	If AE persists for 12 weeks without resolution following reduction in dose Permanent discontinuation from study treatment should be considered for any severe or life-threatening event

If toxicity is attributed to MK-7162, and requires a treatment hold and does not resolve to Grade 0-1 within 12 weeks after the last treatment, then MK-7162 should be discontinued.

With Investigator and Sponsor agreement, participants with a laboratory adverse event still at Grade 2 after 12 weeks may continue treatment in the trial only if asymptomatic and controlled.

After any Grade 4, drug-related adverse event, participants should not restart study treatment without consultation with the Sponsor (Toxicity must have resolved to Grade 0-1 or baseline prior to restarting).

Pembrolizumab treatment will be modified for the adverse events described Section 7.2.4.2.

